The change in IRLS score at each point of evaluation in the FAS, which was the primary endpoint of the study, is shown in Table 7. The mean (standard deviation) change in IRLS score at the end of treatment period was -9.1 (5.7), showing improvement in IRLS score. In terms of the secondary endpoints, the ICGI and PCGI responder rates increased over time, and at the responder rate at the end of treatment period, the ICGI responder rate was 68.4% and the PCGI responder rate was 78.9%.

In moderate to severe idiopathic RLS patients with moderate renal impairment, gabapentin enacarbil once daily 300 mg demonstrated symptomatic improvement of RLS.

Table 7: Change in IRLS score at each time point of evaluation: FAS

	Week 1	Week 2	Week 4	End of treatment period	Follow-up period
n	19	18	18	19	19
Mean	-4.4	-8.1	-9.4	-9.1	-7.4
standard deviation	5.8	5.9	5.6	5.7	7.1
Minimum	-14	-22	-22	-22	-24
Q1	-9.0	-11.0	-12.0	-12.0	-11.0
Median	-4.0	-6.5	-9.0	-9.0	-8.0
Q3	-2.0	-5.0	-7.0	-4.0	0.0
Maximum	8	0	-1	-1	3

The incidence of AEs in this study was 63.2% (12/19 subjects, 19 events). The incidence of AEs for which a causal relationship to the study drug was not ruled out was 36.8% (7/19 subjects, 11 events). There were no deaths or SAEs in this study. AEs leading to discontinuation of study treatment were reported in 2 subjects, of which a causal relationship to the study drug was not ruled out in 1 subject. The event severity was moderate for 1 event of rash in 1 subject, and all other 18 AEs were mild.

Relatively common AEs with an incidence of $\geq 10\%$ were somnolence (15.8%, 3/19 subjects) and blood creatine phosphokinase increased (10.5%, 2/19 subjects). The only relatively common AE for which a causal relationship to the study drug was not ruled out was somnolence (15.8%, 3/19 subjects).

There were no deaths or SAEs. Laboratory test values showed no clinically relevant changes. In summary of the above, the safety and tolerability of gabapentin enacarbil 300 mg once daily in moderate to severe idiopathic RLS patients with moderate renal impairment raised no major concerns.

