7.1 Sample Size

180 subjects per group (360 subjects in the two groups) as participants in the treatment period

[Rationale for the sample size]

The Japanese phase II/III study [CL-0003] demonstrated the change in IRLS score (mean and standard deviation) at the end of treatment period (Week 12) as shown in Table 8. Of the randomized subjects, 11.8% in the placebo group and 17.5% in the 600 mg group were discontinued during the treatment period.

Table 8: Change in IRLS score (mean and standard deviation) at the end of treatment period (i.e., Week 12 of study treatment) in the Japanese phase II/III study [CL-0003]: FAS

	Placebo		ASP8825 600 mg	
	N	Mean (SD)	N	Mean (SD)
Week 12 (LOCF)	116	-8.96 (7.286)	120	-11.10 (7.921)
Week 12 (Treatment period completers)	105	-9.27 (6.996)	98	-11.54 (7.793)

SD: Standard Deviation. LOCF: Last Observation Carried Forward

In addition, a repeated measures analysis of variance of the data from the patients given placebo or ASP8825 600 mg in the Japanese phase II/III study [CL-0003] and included in the

Full Analysis Set showed that the adjusted means of the change from baseline in IRLS score at the end of treatment period (Week 12) were -9.15 in the placebo group and -11.71 in the 600 mg group. The difference between the adjusted means from the two groups was -2.56 .

On the basis of these results, the difference between treatment groups in the change from baseline in IRLS score at the end of treatment period (Week 12) as the primary endpoint of this study was assumed to be -2.56 , with a standard deviation of 8.000 in both groups. Under these assumptions, to detect a statistically significant difference between gabapentin enacarbil and placebo using a 2-sample t-test with a two-sided significance level of 0.05 and a power of 80% , 155 subjects per group would be required. Assuming the discontinuation rate during the treatment period was approximately 15.0% in each group, the sample size has been set to 180 per group.

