## **7.4 Analysis of Efficacy**

### **7.4.1 Analysis of Primary Endpoint**

#### **7.4.1.1 Primary Analysis**

The primary analysis will be performed using the FAS.

The primary efficacy endpoint is the change from baseline in IRLS score at the end of treatment period. Using a repeated measures analysis of variance model, so-called Mixed Model of Repeated Measurements (MMRM) model, having the following average structure, the adjusted mean in each treatment group and its difference (gabapentin enacarbil group - placebo group) at the end of treatment period (Week 12) will be calculated, with comparison between the placebo group and the gabapentin enacarbil group:

Change in IRLS score at each time point

$$= \text{Baseline IRLS score} + \text{Age category}^{\ast 1} + \text{Estimated creatinine clearance category}^{\ast 2} + \\ \text{Treatment group} + \text{Time point} + \text{Treatment group} \times \text{Time point}$$

$\ast^1$  Age category: < 50 years and  $\geq$  50 years

$\ast^2$  Estimated creatinine clearance category:  $\geq$  60 to < 90 mL/min and  $\geq$  90 mL/min

Compound symmetry will be used as the covariance structure for repeated measures of the response variable. A two-sided significance level of 0.05 will be used for statistical tests.

The least-squares mean estimates of the change from baseline in IRLS score at Week 12, the estimates of treatment effect (e.g., least-squares mean change from baseline in IRLS score for gabapentin enacarbil group minus the least-squares mean change from baseline in IRLS score for placebo group) and the corresponding 95% CIs will be reported.

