## **MMRM**

The SAS procedure will be similar to the following:

```
proc mixed;  
  class SUBJECT GROUP VISIT AGE ECC;  
  model CHANGE = GROUP BASE VISIT AGE ECC GROUP*VISIT / ddfm=sat;  
  repeated VISIT /subject = SUBJECT type = cs;
```

```
lsmestimate  
  GROUP*VISIT  
  "GABAPENTIN ENACARBIL v.s. PLACEBO"  
  0 0 ... 0 1 0 0 ... 0 1 / cl alpha=0.05 om;  
  where VISIT in ('Week1', 'Week2', ... , 'Week12');  
run;
```

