### **7.4.1.3 Sensitivity Analysis**

The primary endpoint will be analyzed using the following approaches:

- Analysis of Covariance (ANCOVA) model with Last Observation Carried Forward (LOCF),
- Analysis of Covariance (ANCOVA) model with Multiple Imputation (MI), and
- Pattern Mixture Model (PMM) with different assumptions for missing patterns.

For all sensitivity analyses, confidence intervals will be presented.

Table 5 summarizes all sensitivity analyses to be performed with the primary endpoint.

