### **ANCOVA with MI**

The MI ANCOVA model will be used to compare gabapentin enacarbil and placebo group in a fixed sequence procedure:

1. Generate 1000 datasets, using seed 394852, where intermittent missing IRLS score will be imputed for each treatment relying on non-missing data from all subjects within each treatment group using the Monte Carlo Markov Chain (MCMC) imputation model with treatment and the available non-missing IRLS score for each scheduled Week. The MCMC statement in the SAS PROC MI procedure with monotone option will be used. As a result, each dataset will only have missing ending data, or a monotone missing data pattern.
2. For each dataset from step 1, missing ending data (IRLS score up through end of treatment period) will be imputed using seed 394852. As a result, 1000 imputed complete datasets will be generated.
  - Missing data at Week 1 will be imputed using the regression imputation model with the stratification factors, baseline and IRLS score from Week 1, using the SAS PROC MI procedure with the REGRESSION option in the MONOTONE statement.
  - The SAS PROC MI procedure will use data separately from each treatment subjects to impute the missing data for a specific Week (i.e., only those that need the imputation for the Week). Since subjects from the different treatment groups for that Week are excluded from the step, they will not contribute to the imputation for the Week.
  - Repeat for all other scheduled Weeks sequentially (Week 2 to the end of evaluation period). Subjects whose missing data were imputed for previous Weeks will contribute to the imputation for the current Week.

The regression imputation model includes an intercept and the slopes of the IRLS score from previous Weeks and the stratification factors.

3. Analyze each imputed dataset using the ANCOVA using the observed or imputed IRLS score at Week 12. The model will contain terms for baseline IRLS score measurement as a covariate and treatment group and the other stratification factors as fixed effects.
4. Combine estimates from the results of each of the 1000 ANCOVA runs using SAS PROC MIANALYZE.

The least-squares mean estimates of the change from baseline in IRLS score at Week 12, the estimates of treatment effect (e.g., least-squares mean change from baseline in IRLS score for gabapentin enacarbil group minus the least-squares mean change from baseline in IRLS score for placebo group) and the corresponding 95% CIs will be reported.

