### **7.4.2.1 Change from baseline in IRLS score at each time point**

The baseline visit is the measurement at Week 0.

IRLS score and its change from baseline will be summarized by descriptive statistics, by treatment group and visit.

Least square mean difference (gabapentin enacarbil group minus placebo group) of the changes in IRLS score from baseline will be calculated by visit, using ANCOVA model with the baseline value as a covariate. 95% CI and two-sided p-value of the difference will be presented.

Change from baseline in IRLS score will be summarized by subgroups defined in section 7.8.

Following data will be presented graphically by treatment group:

- IRLS score using mean (+/- SD) plot,
- Change in IRLS score from baseline using mean (+/- SD) plot.

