### **7.10.1 Missing Data**

As a general principle, no imputation of missing data will be done. Exception is the primary efficacy endpoint. The following imputations will be performed:

- An MMRM model will be run for the purpose of implicit imputation of missing data by using all the available information from the observed data via the within-patient correlation structure for continuous endpoints with inferential analysis (section 7.4.1.1).
- An ANCOVA model with Last Observation Carried Forward (LOCF), an ANCOVA model with multiple imputations (MI) and PMM models with different missingness patterns assumptions will be run as the sensitivity analysis for the primary analysis (section 7.4.1.3).

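### The only confirmatory test takes its Week 12 standard error from a variance pooled over seven visits (compound symmetry), with no fallback; an unstructured covariance would remove that dependence cheaply.

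*SAP*

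**What the plan says.** SAP 7.4.1.1 defines the primary analysis as a repeated-measures model of change in IRLS score on the FAS, tested at Week 12 at two-sided 0.05. On the covariance it says: "Compound symmetry will be used as the covariance structure for repeated measures of the response variable". Protocol 7.4.1.1 and the protocol synopsis say the same.

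The example SAS code in the SAP has "repeated VISIT /subject = SUBJECT type = cs", with Satterthwaite degrees of freedom. It has no option for empirical standard errors and none for separate covariances by group. Neither document gives a reason for compound symmetry, a check of it, or a fallback.

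SAP 7.10.1 relies on the same structure for missing data. The model is to impute implicitly by "using all the available information from the observed data via the within-patient correlation structure for continuous endpoints with inferential analysis".

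SAP 7.4.1.3 says that "Table 5 summarizes all sensitivity analyses to be performed with the primary endpoint". The table lists LOCF, multiple imputation and five pattern-mixture analyses, each analysed by a Week 12 ANCOVA. No row refits the repeated-measures model under another covariance.

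**The concern.** The confirmatory question concerns one visit, but the standard error that answers it is built from seven. The method is valid at Week 12 only if the Week 12 variance equals the average over visits. If it is larger, the confidence interval is too narrow and type I error exceeds 5%. If it is smaller, the test is conservative and the trial loses power.

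This matters here because the study was set up to verify 600 mg after the primary analysis of CL-0003 did not. Its single confirmatory p-value should not rest on an assumption that the documents neither support nor refute.

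**Working it through.** **The plan's own figure.** With a difference of -2.56, SD 8.000, two-sided 0.05 and 80% power, the exact two-sample t-test needs 154.26 per group, rounded up to 155 as stated. Inflating for 15% dropout, 155 / 0.85 = 182.4, against the planned 180; 180 × 0.85 = 153 completers give 79.7% power. The calculation uses the Week 12 SD only, so it does not depend on compound symmetry and is not in dispute.

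**Formula.** With complete data, the compound-symmetry variance of the Week 12 contrast uses the mean of the seven visit variances. Let r = (root-mean-square SD over the seven visits) / (Week 12 SD). The true two-sided size is then 2 × [1 − Φ(1.96 r)]. Thresholds: r = 0.960 gives 6.0%, r = 0.924 gives 7.0%, r = 1.048 gives 4.0%.

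**What the documents offer as input.**
- CL-0003, Week 12 completers (protocol Table 8): SD 6.996 (n = 105) and 7.793 (n = 98). Pooled: √[(104 × 6.996² + 97 × 7.793²) / 201] = 7.39. No earlier visits are given.
- CL-0103 (protocol Table 7; open-label, 300 mg, 4 weeks, n = 18 to 19): SD 5.8, 5.9 and 5.6 at Weeks 1, 2 and 4, and 5.7 at end of treatment. The Week 4 to Week 1 ratio is 5.6 / 5.8 = 0.97. Its Pitman-Morgan 95% CI is 0.67 to 1.40 if the within-subject correlation is 0.7, and 0.77 to 1.21 if it is 0.9 (both correlations assumed, with normality).

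So the only by-visit SDs look flat but are too imprecise to establish constant variance, and they stop at Week 4.

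**Size on assumed SD paths.** Each path is linear in weeks from Week 1 to Week 12, except the CL-0103 row (5.8, 5.9, 5.6, then 5.7 held). The simulated columns use 180 per arm, the SAP model terms, correlation 0.85 per two weeks, 15% dropout missing at random and 5,000 null trials per path (Monte Carlo SE 0.3 points).

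| SD path | r | Complete data, compound symmetry | Simulated, compound symmetry | Simulated, unstructured |
|---|---|---|---|---|
| flat 8 | 1.000 | 5.0% | 5.8% | 5.6% |
| CL-0103 pattern | 1.005 | 4.9% | not run | not run |
| 7 to 7.39 | 0.972 | 5.7% | 6.1% | 4.7% |
| 7 to 8 | 0.934 | 6.7% | 7.8% | 5.4% |
| 9 to 8 | 1.067 | 3.6% | 4.2% | 4.9% |
| 5.8 to 8 | 0.859 | 9.2% | 10.3% | 5.5% |

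Worked example, 7 to 8: 1.96 × 0.934 = 1.83, and 2 × [1 − Φ(1.83)] = 6.7%. In simulation the mean compound-symmetry SE was 0.816 against a true 0.907; for unstructured it was 0.890 against 0.899. An estimated difference between 1.96 × 0.816 = 1.60 and 1.96 × 0.890 = 1.74 points would be significant under the first and not under the second.

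**Power in the other direction (9 to 8).** With 153 per arm, SE = 8 × √(2/153) = 0.915 and 2.56 / 0.915 = 2.80. Power is Φ(2.80 − 1.96) = 80% with the correct SE, and Φ(2.80 − 1.96 × 1.067) = 76% with the inflated one.

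**What drives it.** With SD flat at 8, compound symmetry gave 5.2% with complete data, and 5.2% with CL-0003 dropout of 11.8% and 17.5%. For 7 to 8 with exchangeable correlation it gave 6.6%. Unequal variance is the cause; decaying correlation adds little.

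**Remedies.** Compound symmetry with sandwich SEs gave 4.7% to 5.5% on all five simulated paths. With SD flat at 8, the mean Week 12 SE was 0.890 unstructured against 0.878 (1.4% larger), and power at -2.56 was 81.0% against 80.9% (2,000 trials).

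**Existing checks.** The multiple-imputation analysis (S2) was approximated with 25 imputations instead of 1,000. It held 4.6% to 5.3% on all five paths. For 7 to 8, compound symmetry was significant and S2 was not in 3.1% of null trials, with the reverse in 0.3%; for flat 8 the figures were 1.3% and 0.7%.

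**The case against.** The strongest reply is that no defect is shown. Nothing in the documents indicates that the variance changes over visits, and the only by-visit SDs are flat and imply a size of 4.9%. The only rising path with a documented end point (7 to 7.39) gives 5.7%, and its starting value is assumed. The rise from 5.8 to 8 has no support. All of this stands, and it limits the severity. It does not show that the variance is constant. Simulation noise is also not negligible: the unstructured fit itself ranged from 4.7% to 5.6%, so the small excess on the mildest path rests on the formula more than on the simulation.

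Second, the plan already contains analyses free of compound symmetry. S2 says "Analyze each imputed dataset using the ANCOVA using the observed or imputed IRLS score at Week 12", and the by-visit comparison of IRLS change in SAP 7.4.2.1 "will be calculated by visit, using ANCOVA model with the baseline value as a covariate". A result driven by the covariance would therefore be visible. But neither analysis replaces the primary test, so a significant primary with a non-significant S2 would still be the formal finding. The further robustness analysis promised in SAP 7.4.1.2 is not defined.

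Third, the standard-error type is inferred from code offered only as an approximate example. That is true, but no text asks for robust standard errors.

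Fourth, the structure was set in the protocol and carried unchanged into the SAP, which protects against a late choice of covariance. That is a real merit, and it is why any change must be made and dated before unblinding.

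**Conclusion.** The concern holds as a conditional, two-sided risk that should be fixed; confidence is medium. The size of the confirmatory test depends on a variance path that the documents do not report. For modest departures with complete data it runs from about 3.6% (9 falling to 8) to 6.7% (7 rising to 8). It is essentially nominal if the SD is flat, and reaches 9% to 10% only on a steep rise that no document supports. The paths, correlations and dropout mechanism are assumptions; the formula linking r to size is exact only for complete data and large samples. The stated sample size is unaffected.

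**What to change.** Before unblinding, change SAP 7.4.1.1 and its code, protocol 7.4.1.1 and the protocol synopsis as follows.

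- Primary: unstructured covariance with Kenward-Roger degrees of freedom (`type=un`, `ddfm=kr`).
- Fallback if it does not converge: compound symmetry with empirical (sandwich) standard errors, with the degrees-of-freedom method stated. This repairs the standard error but keeps the compound-symmetry working covariance for the implicit handling of missing data, so it should remain a fallback.
- Keep the current compound-symmetry fit as an added row in SAP Table 5.

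No new data are needed. The model has 7 × 8 / 2 = 28 covariance parameters instead of 2, which 360 subjects can support. The cost is a dated SAP revision and a protocol amendment, which may need IRB approval or notification under protocol 8.3.3. If the SD is flat the Week 12 standard error is about 1.4% larger, and the p-value may turn out less favourable than under the current model. If the code has already been broken, the unstructured fit can only be supportive and must be justified in the study report.

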## **MMRM**

The SAS procedure will be similar to the following:

```
proc mixed;  
  class SUBJECT GROUP VISIT AGE ECC;  
  model CHANGE = GROUP BASE VISIT AGE ECC GROUP*VISIT / ddfm=sat;  
  repeated VISIT /subject = SUBJECT type = cs;
```

```
lsmestimate  
  GROUP*VISIT  
  "GABAPENTIN ENACARBIL v.s. PLACEBO"  
  0 0 ... 0 1 0 0 ... 0 1 / cl alpha=0.05 om;  
  where VISIT in ('Week1', 'Week2', ... , 'Week12');  
run;
```

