The primary efficacy endpoint is the change from baseline in IRLS score at the end of treatment period. Using a repeated measures analysis of variance model having the following average structure, the adjusted mean in each treatment group and its difference (gabapentin enacarbil group – placebo group) at the end of treatment period (Week 12) will be calculated, with comparison between the placebo group and the gabapentin enacarbil group:

Change in IRLS score at each time point

= IRLS score at baseline + Age category*¹⁾ + Estimated creatinine clearance category *²⁾ + Treatment group + Time point + Treatment group × Time point

*¹⁾Age category: < 50 years and ≥ 50 years

*²⁾Estimated creatinine clearance category: ≥ 60 to < 90 mL/min and ≥ 90 mL/min

Compound symmetry will be used as the covariance structure for repeated measures of the response variable. A two-sided significance level of 0.05 will be used for statistical tests.

Pharmacokinetics:

No pharmacokinetic evaluation will be performed.

Pharmacodynamics:

No pharmacodynamic evaluation will be performed.

Safety:

Using safety analysis set, the following analyses will be performed by treatment group:

• Adverse events

The frequency of AEs will be tabulated. In addition, AEs will be summarized by System Organ Class (SOC) and Preferred Term (PT) of the the Medical Dictionary for Regulatory Activities (MedDRA).

• Vital signs, laboratory test values, body weight, and Epworth Sleepiness Scale

[figure not shown]
The measured value and its change from baseline at each time point will be summarized using descriptive statistics. The frequency will be tabulated as needed.

Interim analysis:

Not applicable.

V FLOW CHART AND SCHEDULE OF ASSESSMENTS

Flow Chart

- * Subjects using the following drugs before the start of the run-in period will require the specified washout period:
 1. Dopamine agonists, dopamine preparations, gabapentin, pregabalin: ≥ 7 days
 2. Opioids, benzodiazepines (for only if used to treat RLS), long-acting dopamine agonists: ≥ 14 days
- ** For the subjects discontinued during the treatment period, the tests/observations required at discontinuation will be performed and then post-treatment follow-up will be performed as far as possible, but this does not require the use of placebo during the follow-up period.

< Start and end of the post-marketing clinical study >

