The change from baseline in IRLS score at final evaluation in the MITT analysis set, which was a primary endpoint of the study, is shown in Table 4. A paired comparison between the placebo group and the gabapentin enacarbil group showed a statistically significant difference ($P = 0.0003$; analysis of covariance adjusted for pooled study site and baseline).

Table 4: Change from baseline in IRLS score at Week 12 using LOCF (MITT analysis set)

	Placebo n = 108	XP13512* n = 112	Mean difference (XP13512 group – placebo group)	95% CI
	Mean (SD)	Mean (SD)		
Baseline	22.6 (4.91)	23.1 (4.86)		
Week 12	13.8 (7.47)	9.8 (8.70)		
Change from baseline	-8.8 (8.63)	-13.2 (9.21)	-4.0	-6.2, -1.9

*Gabapentin enacarbil

The ICGI responder rate at final evaluation, which was another primary endpoint of the study, was 38.9% (42/108 subjects) in the placebo group and 76.1% (83/109 subjects) in the gabapentin enacarbil group with an odds ratio [95% confidence interval] of 5.1 [2.8, 9.2], showing a statistically significant difference between the placebo group and the gabapentin enacarbil group ($P < 0.0001$; logistic regression analysis model with treatment group and pooled study site as explanatory variables).

AEs (including abnormal laboratory test values) were reported in 74.1% (80/108 subjects) in the placebo group and 82.3% (93/113 subjects) in the gabapentin enacarbil group. There were no deaths. An SAE other than deaths was reported in 1 subject in the placebo group (appendicitis), for which a causal relationship to the study drug was ruled out.

AEs for which a causal relationship to the study drug was not ruled out were reported in 40.7% (44/108 subjects) in the placebo group and 70.8% (80/113 subjects) in the gabapentin enacarbil group. Common events included somnolence (8 subjects in the placebo group, 29 subjects in the gabapentin enacarbil group), dizziness (3 subjects in the placebo group, 20 subjects in the gabapentin enacarbil group), headache (8 subjects in the placebo group, 14 subjects in the gabapentin enacarbil group), fatigue (2 subjects in the placebo group, 11 subjects in the gabapentin enacarbil group), and nausea (2 subjects in the placebo group, 9 subjects in the gabapentin enacarbil group).

As an AE related to vital signs (blood pressure, pulse rate, respiratory rate, and body temperature), orthostatic hypotension was reported in 1 subject in the gabapentin enacarbil group.

ECG showed no clinically relevant abnormal findings.

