### **4 SAMPLE SIZE**

180 subjects per group (360 subjects in the two groups) as participants in the treatment period.

[Rationale for sample size]

The Japanese phase II/III study [CL-0003] demonstrated the change in IRLS score (mean and standard deviation) at the end of treatment period (Week 12) as shown in Table 1. Of the randomized subjects, 11.8% in the placebo group and 17.5% in the 600 mg group were discontinued during the treatment period.

**Table 1: Change in IRLS score (mean and standard deviation) at the end of treatment period (i.e., Week 12 of study treatment) in the Japanese phase II/III study [CL-0003]: FAS**

	Placebo		ASP8825 600 mg	
	N	Mean (SD)	N	Mean (SD)
Week 12 (LOCF)	116	-8.96 (7.286)	120	-11.10 (7.921)
Week 12 (Treatment period completers)	105	-9.27 (6.996)	98	-11.54 (7.793)

SD: Standard Deviation. LOCF: Last Observation Carried Forward

In addition, a repeated measures analysis of variance of the data from the patients given placebo or ASP8825 600 mg in the Japanese phase II/III study [CL-0003] and included in the Full Analysis Set showed that the adjusted means of the change from baseline in IRLS score at the end of treatment period (Week 12) were -9.15 in the placebo group and -11.71 in the 600 mg group. The difference between the adjusted means from the two groups was -2.56.

On the basis of these results, the difference between treatment groups in the change from baseline in IRLS score at the end of treatment period (Week 12) as the primary endpoint of this study was assumed to be -2.56, with a standard deviation of 8.000 in both groups. Under these assumptions, to detect a statistically significant difference between gabapentin enacarbil and placebo using a 2-sample t-test with a two-sided significance level of 0.05 and a power of 80%, 155 subjects per group would be required. Assuming the discontinuation rate during the treatment period was approximately 15.0% in each group, the sample size has been set to 180 per group.

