**Table 5 Primary, Secondary and Sensitivity Analyses for Primary Endpoint**

Code	Set	Endpoint	Model	Covariates
Primary	FAS	Change from baseline in IRLS score at the end of treatment period (Week 12)	MMRM	Treatment group, Visit, Baseline IRLS score, Age category, Estimated creatinine clearance category, Visit by Treatment group interaction
Secondary	PPS	Change from baseline in IRLS score at the end of treatment period (Week 12)	MMRM	Treatment group, Visit, Baseline IRLS score, Age category, Estimated creatinine clearance category, Visit by Treatment group interaction
S1	FAS	Change from baseline in IRLS score at the end of treatment period (Week 12)	ANCOVA with LOCF	Treatment group, Baseline IRLS score, Age category, Estimated creatinine clearance category
S2	FAS	Change from baseline in IRLS score at the end of treatment period (Week 12)	ANCOVA with MI	Treatment group, Baseline IRLS score, Age category, Estimated creatinine clearance category
S3	FAS	Change from baseline in IRLS score at the end of treatment period (Week 12)	PMM (Last Mean Carried Forward)	Treatment group, Baseline IRLS score, Age category, Estimated creatinine clearance category
S4	FAS	Change from baseline in IRLS score at the end of treatment period (Week 12)	PMM (Last Mean Carried Forward for Gabapentin Enacarbil and Randomized Arm MAR for Placebo)	Treatment group, Baseline IRLS score, Age category, Estimated creatinine clearance category
S5	FAS	Change from baseline in IRLS score at the end of treatment period (Week 12)	PMM (Copy Reference)	Treatment group, Baseline IRLS score, Age category, Estimated creatinine clearance category
S6	FAS	Change from baseline in IRLS score at the end of treatment period (Week 12)	PMM (Jump to Reference)	Treatment group, Baseline IRLS score, Age category, Estimated creatinine clearance category
S7	FAS	Change from baseline in IRLS score at the end of treatment period (Week 12)	PMM (Copy Increment from Reference)	Treatment group, Baseline IRLS score, Age category, Estimated creatinine clearance category

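### The primary MMRM applies one baseline IRLS slope to all seven visits; a baseline-by-visit term would guard the Week 12 comparison at almost no cost

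*SAP*

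**What the plan says.** The SAS code in SAP 7.4.1.1 fits "model CHANGE = GROUP BASE VISIT AGE ECC GROUP*VISIT / ddfm=sat". BASE is not a CLASS variable, so it has a single linear slope, and the only interaction is treatment by visit. Table 5 lists the same terms for the Primary (FAS) and Secondary (PPS) rows: "Treatment group, Visit, Baseline IRLS score, Age category, Estimated creatinine clearance category, Visit by Treatment group interaction". The mean model in the protocol synopsis and in Protocol 7.4.1.1 matches and begins "IRLS score at baseline + Age category".

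The code selects visits with "where VISIT in ('Week1', 'Week2', ... , 'Week12"; the window table in SAP 7.10.3.1 shows these to be Weeks 1, 2, 4, 6, 8, 10 and 12. On covariance the SAP states: "Compound symmetry will be used as the covariance structure for repeated measures of the response variable".

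The other Week 12 comparisons are built differently. S1 to S7 end in an ANCOVA of the Week 12 endpoint alone (Table 5; SAP 7.4.1.3), and SAP 7.4.2.1 plans a separate baseline-adjusted ANCOVA at each visit. Neither document gives a reason for holding the slope constant in the MMRM.

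**The concern.** With a main effect only, the regression of change on baseline is forced to be the same at Week 1 and at Week 12. Under compound symmetry with complete data, the fitted slope is the visit average. If subjects with high baseline scores improve more as treatment goes on, the slope at Week 12 is steeper than that average, and the Week 12 difference is only partly adjusted for baseline.

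The premise is reasonable. Response may be incomplete at Week 1: in CL-0103 (Protocol Table 7) mean change was -4.4 at Week 1 and -9.4 at Week 4, and in this trial active subjects with creatinine clearance of 60 to below 90 mL/min take a lower dose in Week 1.

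Two things are at stake. One is a little precision. The other is a possible shift in the estimate if the arms lose subjects with different baseline severity. Such a shift would also blur the sensitivity analyses. S1 to S7 are meant to probe missing data, but they differ from the primary model in the baseline slope as well.

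**Working it through.** **1. The plan's own figure.** The SAP takes an effect that "was assumed to be -2.56, with a standard deviation of 8.000 in both groups" and concludes, "using a 2-sample t-test with a two-sided significance level of 0.05 and a power of 80%, 155 subjects per group would be required". Normal approximation: 2 × (1.960 + 0.842)² × 8² / 2.56² = 153.3, so 154. With the noncentral t, power is 0.7993 at 154 and 0.8019 at 155, so 155 reproduces. Inflation gives 155 / 0.85 = 183 or 155 × 1.15 = 179; the stated 180 is close to both. None of this depends on the baseline slope.

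**2. Week 12 slopes implied by Protocol Tables 4 and 5.** Covariance = (SD_base² + SD_wk12² − SD_change²) / 2; slope of change on baseline = covariance / SD_base² − 1.
- XP052 placebo: (4.91² + 7.47² − 8.63²) / 2 = 2.72; 2.72 / 24.11 − 1 = -0.89
- XP052 active: (4.86² + 8.70² − 9.21²) / 2 = 7.24; 7.24 / 23.62 − 1 = -0.69
- XP053 placebo: (4.58² + 7.87² − 7.69²) / 2 = 11.89; 11.89 / 20.98 − 1 = -0.43
- XP053 1200 mg: (5.32² + 8.03² − 9.12²) / 2 = 4.80; 4.80 / 28.30 − 1 = -0.83

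The baseline to Week 12 score correlations are 0.07 to 0.33. Slopes at earlier visits cannot be derived from the documents.

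**3. Effect of a slope gap under chance imbalance.** Assume a baseline SD of 5 (the four overseas arms run from 4.58 to 5.32). With 180 per arm the baseline difference has SD 5 × √(2/180) = 0.53. Shift in the Week 12 difference = gap × imbalance. Take a Week 12 slope of -0.7, so the residual SD is √(64 − 0.7² × 25) = 7.19 and the SE with the correct slope is 7.19 × √(2/180) = 0.758.
- Gap 0.2: shift 0.11 points per 1-SD imbalance; SE × 1.010; power 92.2% to 91.7%
- Gap 0.4: shift 0.21 points per 1-SD imbalance; SE × 1.038; power 92.2% to 90.2%

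**4. Early plateau.** Suppose slopes follow the Table 7 means and are flat from Week 4. The ratio of pooled to Week 12 slope is (4.4/9.4 + 8.1/9.4 + 5) / 7 = 0.90. For Week 12 slopes of -0.7 to -0.89 the gap is 0.07 to 0.085, a shift of about 0.035 to 0.045 points per 1-SD imbalance. The variance rises by only about 0.2-0.3%.

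**5. Simulation of the planned model** (180 per arm, compound-symmetry residuals with correlation 0.6, 14-15% dropout missing at random, true effect -2.56, 3000 trials per scenario):

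| Assumed slope path | Slope applied at Week 12, without / with the term | Empirical SE, without / with | Power, without / with |
|---|---|---|---|
| Constant -0.5 | -0.50 / -0.50 | 0.801 / 0.801 | 88.5% / 88.4% |
| -0.2 to -0.7 | -0.47 / -0.70 | 0.813 / 0.801 | 87.9% / 88.4% |
| -0.1 to -0.9 | -0.51 / -0.90 | 0.836 / 0.801 | 87.2% / 88.3% |

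The mean error was at most 0.04 points with or without the term, and type I error was 5.5-5.8% under both models. Separate runs on a -0.15 to -0.89 path gave a variance 4-15% larger without the term, depending on dropout (SE about 2-7% larger).

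**6. Dropout that depends on baseline differently by arm.** CL-0003 discontinuation was 11.8% and 17.5% (Protocol 7.1). The dependence on baseline is assumed, and deliberately strong here (odds ratio 2.2 per SD in the active-only case; 600 trials per scenario; true effect -2.56):

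| Dropout rises with baseline in | Slope path | Planned model | With the term | Shift |
|---|---|---|---|---|
| Active arm only | Early plateau | -2.46 | -2.57 | 0.11 |
| Active arm only | Steep | -2.19 | -2.58 | 0.39 |
| Opposite directions by arm | Early plateau | -2.35 | -2.55 | 0.20 |
| Opposite directions by arm | Steep | -1.81 | -2.48 | 0.67 |

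Weaker dependence gave 0.02 to 0.08 (early plateau) and 0.12 to 0.18 (steep). A milder opposite-direction case gave 0.11 and 0.26. With a flat slope the two models agree.

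**The case against.** A common-slope model is a legitimate choice, and protocol and SAP specify it consistently. A reader might infer from Tables 4 and 5 that the pooled slope is wrong at Week 12. The documents do not show that: it needs slopes by visit, and none are given. The Week 12 slopes are themselves weak guides. They are LOCF figures from non-Japanese subjects, with 1200 mg in the active arms, and the two placebo arms alone give -0.89 and -0.43.

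The only by-visit changes in the documents (Table 7: 19 subjects, uncontrolled, four weeks) point to an early plateau, where the precision gain is about zero. Five of the seven visits fall at Week 4 or later. Nothing in the documents says that dropout depends on baseline IRLS; 11.8% and 17.5% are overall rates.

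The by-visit ANCOVAs and S1 to S7 would also show a discrepancy if one arose. They would not isolate its cause, because S1 to S7 also change the missing-data handling and the by-visit ANCOVAs omit the age and creatinine clearance terms.

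All of this stands as a limit on the size of the point. It does not supply a reason to prefer the constrained model, since the added term costs almost nothing when the slope is constant.

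**Conclusion.** The point holds as a minor, conditional one. The constraint is certain; its misfit at Week 12 is not. Chance imbalance causes no average bias. The SE penalty is nil with a flat slope or early plateau and about 1-4% for slope gaps of 0.2 to 0.4, somewhat more in some runs on the steepest path. If dropout depends on baseline differently by arm, the estimate can move by roughly 0.05 to 0.3 points even though the data are missing at random given baseline. Larger shifts (0.39 and 0.67) appeared only when strong dependence was combined with a steep slope, and the largest needed opposite directions in the two arms. These sizes rest on a baseline SD of 5, the assumed slope paths and the assumed dropout models.

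Two further inferences should be resisted. The FAS primary analysis is not the only Week 12 comparison with this constraint, because the PPS MMRM shares it. Nor does the missing term explain inflated type I error: in runs where residual SD rose and correlation decayed over time, rejection under the null was about 7-10% with or without the term. That comes from compound symmetry, and this change does not cure it.

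**What to change.** Add Baseline IRLS × Time point to the primary model in the protocol synopsis, Protocol 7.4.1.1 and SAP 7.4.1.1. Add BASE*VISIT to the MODEL statement, and add the term to the Primary and Secondary rows of Table 5. If the constant slope is kept, state why.

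The cost is an amendment to both documents before the treatment code is broken, plus 7 − 1 = 6 degrees of freedom out of at most 360 × 7 = 2,520 observations. With a constant slope the simulated SE was unchanged at 0.801.
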